9.3 Procedures at Each Visit

9.3.1 Screening (Visit 1)

Eligible patients will be informed about the ongoing study by the PI or by an involved practitioner, and will be handed out study patient information including informed consent form.

9.3.2 Baseline (Visit 2)

9.3.2.1 Admission Interview

Eligible Patients giving oral consent to study participation will be interviewed by the SN for detailed screening of inclusion/exclusion criteria. A patient information eCRF will be filled covering all necessary points for temporary admission of the patient into the study. Definite admission can only be acquired after the surgery. The signed informed consent form will be validated by signature by the PI and stored in the patient's trial file. The patient will receive a copy of the signed informed consent form. For female patients of child bearing potential, a pregnancy test will be performed. The result of the pregnancy test will be photographed and the photograph will be signed by the PI and filed. The patient will be given the opportunity to clarify all uncertainties concerning the trial and the upcoming surgery with the PI. Also recorded will be the medical history and patient demographics. At this stage the preinjury activity level using Tegner activity scale will be assessed.

9.3.2.2 Preoperative Clinical Examination

Clinical examination will be conducted by the PI. The following information will be recorded in the eCRF:

- Date of examination.
- Intra/Extra-articular effusion.

- Knee mobility.
- Anterior displacement of the affected and of the healthy knee using the Lachman Test and the KT-1000 Arthrometer Test.
- Online survey for all patient-completed questionnaires (IKDC SKEF, LKSS and TAS)
- Rotational stability of both knees using the Pivot shift test.

9.3.2.3 Surgical Intervention

9.3.2.3.1 Surgery

See chapter 8.

9.3.2.3.2 Randomization

Patient randomization is acquired intraoperatively only if all inclusion criteria and no exclusion criteria have been met. The folded tendon-graft (not sutured, without OCS) must measure 8 – 8.5 mm in diameter at the end which is to be inserted into the femoral bone tunnel. If no intraoperatively assessed exclusion criteria are met (e.g. tendon-graft specifications, severe cartilage damage, extensive meniscus resection necessary) the subject is allocated to one of the two treatment groups. The envelope for the randomized group allocation of the subject is opened and the surgical procedure is carried out respectively. The envelope is sealed again afterwards and stored in the patient's trial file. The randomization procedure is described in detail in ACLROCS_WI_Randomization.

9.3.2.3.1 CT-Scan

The CT-scan will be performed according to ACLROCS_WI_CTSscan.

9.3.2.3.2 Plain Radiography

Standard posteroanterior radiographs of the knee in full extension will be performed [ACLROCS_WI_PlainRadiography].

9.3.3 Follow-up 1 (Visit 3)

Follow-up 1 will be performed 42 days after surgery. The patient will be asked to fill an online survey for all patient-completed questionnaires (IKDC SKEF, LKSS and TAS) in the clinic. Subsequently, the clinical examination is conducted by the PI recording the identical points as during the preoperative clinical examination and the occurrence of any potential AEs. Plain radiography measurement is performed according to ACLROCS_WI_PlainRadiography.

9.3.4 Follow-up 2 (Visit 4)

Follow-up 2 will be performed equivalently to Follow-up 1. Additionally, CT-scanning is performed according to ACLROCS_WI_CTSscan. This WI includes pregnancy testing and its validation by signature by the PI before the CT-scan. Follow-up 2 will be performed 4.5 months after surgery.

9.3.5 Follow-up 3 (Visit 5)

Follow-up 3 will be performed equivalently to Follow-up 2. It will be performed 1 year after surgery.

9.3.6 Follow-up 4 (Visit 6)

At Follow-up 4 patient-completed questionnaires and clinical examination will be performed equivalently to Follow-up 2 and 3. A plain radiography measurement (pregnancy test) will be done. No CT-scan will be performed. It is scheduled 2 years after surgery.

9.3.7 Follow-up 5 (Visit 7)

At Follow-up 5 no CT-scan and no plain radiography will be performed. Patient-completed questionnaires and clinical examination will be done equivalently to Follow-up 2 and 3. Additionally, the study-end eCRF will be filled-out. It is scheduled 5 years after surgery.

10 SAFETY

10.1 Medical Device Category A studies

10.1.1 Definition and Assessment of safety related events

Adverse Event (AE)

Any untoward medical occurrence, unintended disease or injury or any untoward clinical signs (including an abnormal laboratory finding) in participants, users or other persons whether or not related to the investigational medical device [ISO 14155: 3.2].

Serious Adverse Event (SAE)

Adverse event that:

- results in death, or
- led to a serious deterioration in health that either:
 - results in a life-threatening illness or injury, or
 - results in a permanent impairment of a body structure or a body function, or
 - required in-patient or prolonged hospitalisation, or
 - results in medical or surgical intervention to prevent life threatening illness, or
- led to fetal distress, death or a congenital abnormality or birth defect. [ISO 14155: 3.37].

Health hazards that require measures

Findings that may require additional action are:

- Persistent anterior knee pain
- Septic arthritis
- Arthrofibrosis
- Graft rupture
- Aseptic effusion
- Subcutaneous cyst

10.1.2 Reporting of Safety related events

Reporting to Authorities:

In Category A studies it is the Investigator's responsibility to report to the local Ethics Committee

- **Health hazards** that require measures within 2 days

11 STATISTICAL METHODS

11.1 Hypothesis

Null hypothesis: Both treatments yield the same relative change in bone tunnel volume from baseline (Visit 2) to follow-up 3 (Visit 5).

$$\mu_{\text{Control}} = \mu_{\text{Intervention}}$$

Alternative hypothesis: The two treatments have a different effect on the primary endpoint after entire follow-up

$$\mu_{\text{Control}} \neq \mu_{\text{Intervention}}$$

11.2 Determination of Sample Size

For the power calculation a dedicated software (G*Power [84]) was used. It is aimed to detect a 20% difference in relative change of bone tunnel volume between the two groups. Pooling the standard deviations of the percentage volume change of different bone tunnel sections (articular/outside third) and two different tunnels (anteromedial/posterolateral tunnel) from the study conducted by Araki et al. [85] yields an estimate for the overall standard deviation of $\pm 25.175\%$. With a type I error rate of $\alpha=0.05$ and a power of $1-\beta = 0.8$ and assuming both samples to be normally distributed and having equal variances, the required sample size per group is $n = 25$.

Accounting for a drop-out rate of 10% the total number of subjects for equally sized groups to be acquired is $N = 56$.

11.2.1 Power calculation of secondary outcome variables

Based on the calculated sample size above (expected drop-out excluded), power calculations for the secondary variables to be used for statistical inference testing are conducted. The table below shows the results of the power calculation of primary and secondary outcome variables.

	Tunnel Enlargement	IKDC Subjective Knee Evaluation Form	Lysholm Knee Scoring Scale	KT-1000 Arthrometer Test	Lachman Test	Pivot Shift Test
Test significance level, α	0.05	0.05	0.05	0.05	0.05	
Assumption of distribution	Normal	Normal	Normal	Non-normal	Non-normal	Non-normal
Difference in means to be detectable $ \mu_{\text{Control}} - \mu_{\text{Intervention}} $	20% [86]	11.5 [87]	10 [88]	2 mm	0.5	0.8
Common standard deviation, σ	25.175% [85]	10 [86]	7 [86]	1.7 mm [86]	0.25	0.71 [86]
Effect size, $\delta = \mu_{\text{Control}} - \mu_{\text{Intervention}} / \sigma$	0.7944	1.15	1.429	0.88	2	1.13
Power	0.8	0.98	0.99	0.84	0.99	0.97
N per group (identically sized)	25	25	25	25	25	25

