Number of Participants with Rationale:	A total of 56 patients are required to detect a minimal clinically important difference in relative change of bone tunnel volume after a 2-year follow-up of 20% given an assumed standard deviation of 25.2% with a power of 0.8 and an α -error of 0.05 and accounting for a drop-out rate of 10% for this equally sized two-group parallel design.
Study Duration:	Expected duration for patient acquisition: 22 months Expected time from first patient acquisition to the end of follow-up of the last patient: 82 months Statistic and Abstract: ca. 6 months
Study Schedule:	First-Patient-In: 07/2017 Last-Patient-Out: 05/2024 Statistics/Abstract: 12/2024
Investigator(s):	PD Dr. med. [name] University Hospital Balgrist
Study Centre(s):	University Hospital Balgrist
Statistical Considerations:	Intention-To-Treat analysis Independent t-test on the primary efficacy outcome comparing the two groups with a significance level of 0.05, 2-sided.
GCP Statement:	This study will be conducted in compliance with the protocol, the current version of the Declaration of Helsinki, the ICH-GCP or ISO EN 14155 (as far as applicable) as well as all national legal and regulatory requirements.

STUDY SUMMARY IN LOCAL LANGUAGE

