5 STUDY OUTCOMES

5.1 Primary Outcome

The primary outcome variable of this study is the relative change of the CT evaluated femoral bone tunnel volume from baseline to follow-up at 12 months.

As the primary objective of the use of the OCS is to reduce tunnel widening by promoting bony ingrowth into the bone tunnel, the relative change of bone tunnel volume over time is an appropriate measure to quantitatively assess this effect. Assessing relative changes as opposed to absolute values negates the potential for bias by different tunnel drill sizes used in the two treatment arms potentially influencing the absolute ossification/de-ossification. In quantifying bone tunnel size, CT measurements provide substantially more reliable means than plain radiography or magnetic resonance imaging [50, 68].

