5.2.2.2 Lachman Test

The Lachman test measures anterior displacement conducted manually by the clinician. It is graded as the difference from the normal contralateral side as 0 (<3 mm), 1 (3 to 5 mm), or 2 (>5 mm) [74].

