6.1.1 Time Frame of the Study

Currently, no precise time frame for the occurrence of BTW has been defined [41]. Chen et al. [77] investigated the incidence of BTW following ACL-reconstruction using hamstring tendon in 58 patients at 1, 2, 3, 6, 12 and 24 months postoperatively. BTW was found to mainly occur during 3 to 6 months after surgery with no change in bone tunnel volume between 12 and 24 months postoperatively. Similarly, Jo et al. [78] concluded, BTW to be maximal within the first 9 months following surgery using patellar tendon grafts. For the current trial, BTW-assessment using CT-scanning 4.5 and 12 months after surgery seems therefore reasonable. The need of correlating BTW with long-term clinical results has also been pointed out [79].

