11.4.2.4 Assessment of Knee Stability

The side-to-side difference of the KT-1000 Arthrometer Test will be reported in group mean and standard deviation. The two group means will be compared with the Mann-Whitney U test. The side-to-side difference [86] scores of the Lachman Test and the Pivot Shift Test will be reported in frequencies. Statistical inference testing will be done using the Mann-Whitney U test.

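### Section 11.2.1: the KT-1000 column contradicts itself and the Lachman SD of 0.25 cannot go with a 0.5-grade difference; separately, the synopsis sample-size rationale puts tunnel volume change at 2 years although CT ends at 12 months

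*Combined protocol and SAP*

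**What the plan says.** Section 11.2.1 takes 25 per group, excluding expected drop-out, and states that "power calculations for the secondary variables to be used for statistical inference testing are conducted". It continues: "The table below shows the results of the power calculation of primary and secondary outcome variables". Its table defines effect size as the difference in means divided by the common SD. The two columns at issue read:

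| | Difference | SD | Effect size | Power |
|---|---|---|---|---|
| KT-1000 | 2 mm | 1.7 mm (cited source) | 0.88 | 0.84 |
| Lachman | 0.5 | 0.25 (no source) | 2 | 0.99 |

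The Lachman scale is defined in section 5.2.2.2: "It is graded as the difference from the normal contralateral side as 0 (<3 mm), 1 (3 to 5 mm), or 2 (>5 mm"). Section 9.2.2.2 records the same three grades. Section 11.4.2.4 tests KT-1000 by Mann-Whitney, and for the side-to-side Lachman and Pivot Shift scores it says: "Statistical inference testing will be done using the Mann-Whitney U test".

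On timing, the synopsis row on the number of participants justifies N = 56 by a "minimal clinically important difference in relative change of bone tunnel volume after a 2-year follow-up of 20" per cent. Section 5.1 defines the primary outcome "from baseline to follow-up at 12 months", and section 11.1 states the null hypothesis "from baseline (Visit 2) to follow-up 3 (Visit 5"). Section 6.1.1 says: "BTW-assessment using CT-scanning 4.5 and 12 months after surgery seems therefore reasonable". Section 9.3.6 rules out a CT scan at the 2-year visit.

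**The concern.** The table is the plan's only statement of what the knee-stability tests can detect. Someone interpreting a null KT-1000 or Lachman result would go to it. In one column the entries disagree with each other; in the other, the inputs cannot occur together on the scale used.

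The synopsis problem is separate. The sample-size row is the only place in the synopsis that attaches a time to tunnel volume change, and it names a visit at which the outcome is not measured.

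The stake is limited. The sample size rests on the primary outcome, the confirmatory test is on tunnel volume alone, and the stopping rule uses only the primary outcome.

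**Working it through.** **Inputs.** 25 per group (sections 11.2 and 11.2.1), two-sided 0.05 (section 11.4), and the differences, SDs, effect sizes and powers in the section 11.2.1 table. t-test power is from the noncentral t distribution. Mann-Whitney power uses the same formula with n multiplied by the asymptotic relative efficiency (ARE): 0.955 for normal data, 0.864 as the worst case.

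**Columns that reproduce.**

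- IKDC: 11.5/10 = 1.15; t power 0.979 (table 0.98).
- Lysholm: 10/7 = 1.429; t power 0.999 (table 0.99).
- Pivot Shift: 0.8/0.71 = 1.13; Mann-Whitney power 0.969 (table 0.97).

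The formula and the power method are therefore as the table describes, and the KT-1000 conflict is not a difference of method.

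**KT-1000.** 2/1.7 = 1.176, not 0.88.

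| Effect size | t-test | Mann-Whitney, ARE 0.955 | Mann-Whitney, ARE 0.864 |
|---|---|---|---|
| 0.88 (printed) | 0.862 | 0.845 | 0.806 |
| 1.176 (from 2 mm and 1.7 mm) | 0.983 | 0.978 | 0.965 |

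Simulating the Mann-Whitney test on normal data gives 0.840 at 0.88 and 0.977 at 1.176. So 0.88 and 0.84 agree with each other, but not with 2 mm and 1.7 mm. Two single-entry changes would reconcile the column:

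- Difference of about 1.5 mm at SD 1.7 mm: 0.88 × 1.7 = 1.496, and 1.5/1.7 = 0.882.
- SD of about 2.27 mm at a difference of 2 mm: 2/0.88 = 2.273.

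**Lachman.** The division 0.5/0.25 = 2 is correct; the inputs are the problem. A whole-number score whose mean has fractional part f has variance of at least f(1 − f).

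- SD 0.25 means variance 0.0625. Then f(1 − f) ≤ 0.0625 requires f ≤ 0.067 or f ≥ 0.933, so each arm's mean lies within 0.067 of a whole number. Two such means differ by at most 0.13 or by at least 0.87, never by 0.5.
- Smallest pooled SD: with fractional parts f and f + 0.5, the average of the two minimum variances is least at f = 0, where it is (0 + 0.25)/2 = 0.125. The SD is 0.354 and the effect size at most 0.5/0.354 = 1.41.
- Smallest SD shared by both arms: at f = 0.25 both minimum variances are 0.25 × 0.75 = 0.1875. The SD is 0.433 and the effect size at most 0.5/0.433 = 1.15.

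The bounds hold for any whole-number score, so they also cover a side-to-side difference of grades.

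The plan gives no grade distribution, so the following distributions are assumptions. Each has a mean difference of 0.5. Power is simulated for the tie-corrected Mann-Whitney test, 20,000 runs each.

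| Control, % at grades 0/1/2 | Intervention, % at grades 0/1/2 | Pooled SD | Power |
|---|---|---|---|
| 40/20/40 | 65/20/15 | 0.82 | 0.53–0.54 |
| 30/40/30 | 60/30/10 | 0.72 | 0.66 |
| 20/60/20 | 60/30/10 | 0.65 | 0.78 |
| 35/55/10 | 80/15/5 | 0.58 | 0.88 |
| 45/45/10 | 87/11/2 | 0.55 | 0.90 |
| 25/75/0 | 75/25/0 | 0.43 | 0.95–0.97 |
| 50/50/0 | 100/0/0 | 0.35 | 1.00 |

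These are illustrations, not bounds.

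**Synopsis.** The study schedule lists CT at surgery, 4.5 months and 1 year only. Sections 5.1, 11.1 and 11.4.2 place the primary comparison at 12 months (Visit 5), and section 9.3.6 has no CT at 2 years. The 2-year wording in the sample-size row stands alone against all of these.

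**The case against.** The best case on the other side is that this is editorial. No test, population, visit or decision rule uses these powers, and N is untouched. That is true, and it limits the weight of the point.

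For KT-1000 the direction is harmless: if 2 mm and 1.7 mm are right, the plan understates its power; if 0.88 is right, the 0.84 stands. That also holds. But the reader still cannot tell which difference the test is powered to detect, 1.5 mm or 2 mm.

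For Lachman, the low powers depend on distributions with many controls at grade 2, for which the documents give no basis. If only two adjacent grades occur, power for a 0.5 difference is about 0.95 or more. So it is not shown that power is low. What stands is that SD 0.25 is infeasible and 0.99 has nothing behind it.

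For the synopsis, the outcome row gives no time and the synopsis visit list puts CT at Visits 2, 4 and 5, so the 2-year phrase is one stray statement in the sample-size row. Section 6.1.1 also cites a study with no volume change between 12 and 24 months. The operative text is clear, but the phrase is still wrong.

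The table's primary column could also be questioned: it gives 0.802 by the normal approximation, which matches the stated 0.80 and n = 25, but 0.786 by noncentral t. That is a separate matter and does not bear on these three corrections.

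**Conclusion.** The point holds in all three parts.

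- **KT-1000:** the printed difference and SD give an effect size of 1.18 and Mann-Whitney power of about 0.97 to 0.98, some 13 points above the 0.845 that follows from the printed 0.88. Which entry is at fault cannot be settled from the documents.
- **Lachman:** a common SD of 0.25 with a 0.5 difference is mathematically impossible on whole grades, and this needs no assumption beyond the scale in section 5.2.2.2. The effect size is at most 1.41 (pooled SD) or 1.15 (SD shared by both arms), so 0.99 is unsupported. The true power depends on an unstated grade distribution and could be close to 0.99 or well below it.
- **Synopsis:** the sample-size rationale names a time point at which the primary outcome is not measured.

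The plan should be corrected, but the sample size and the confirmatory analysis are not affected.

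**What to change.** 1. **KT-1000:** check the 1.7 mm against its cited source, establish the intended difference, and restate the column so that difference, SD, effect size and power agree. Power may rise to about 0.98 or stay at 0.84.
2. **Lachman:** state the assumed percentage at each grade in each arm, compute Mann-Whitney power from those distributions, and replace the SD, effect size and power. Otherwise delete the Lachman power claim. The restated power may stay near 0.99 or fall substantially.
3. **Synopsis, number of participants:** replace the 2-year time point with 12 months (Visit 5).

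The cost is wording in one table and one synopsis cell, plus one short power calculation if the Lachman claim is kept. These corrections leave 25 per group and N = 56 as they are, and trial conduct does not change.

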11.3 Statistical Criteria of Termination of Trial

Statistically significant inferiority ($P \leq 0.05$) of the interventional treatment determined at 4.5 months follow-up on the primary efficacy outcome with a total of 20 patients (10 interventional, 10 control) will lead to premature termination of the study.

11.4 Planned Analyses

In all statistical analyses testing a significant difference in central tendency between the two groups, significance is set at $\alpha = 0.05$. All statistical tests will be two-sided. The results of these tests will be reported in 95% confidence Interval and p-value for the Student's t-test and in Mann-Whitney U and p-value for the Mann-Whitney U test.

11.4.1 Datasets to be analyzed, analysis populations

Statistical analysis is based on the intention-to-treat analysis. In the case of the current trial this means that patients not following the rehabilitation protocol will not be excluded from analysis.

11.4.2 Primary Analysis

Confirmatory analysis is performed on the null hypothesis of equal relative changes in bone tunnel volume from baseline to last CT follow-up (follow-up 3, Visit 5) between the two groups. To make appropriate assumptions on the distribution of the data, the Kolmogorov-Smirnov Test is used to test for significant departure from normality. Significance is set at $\alpha = 0.05$. In case the assumption of normality holds, a Student's t-test is performed to test for a significant difference in means between the two groups. In case the normality assumption is violated, a Mann-Whitney U test is applied. Mean values and standard deviations will be reported. The same procedure will be applied on the dataset of the first CT-follow-up (Visit 4) in the mode of a supportive analysis.

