6.3 Methods of Minimizing Bias

6.3.1 Randomization

A two-staged randomization method will be used. To ensure adequate treatment distribution for interim analysis, the first block will contain 10 interventional and 10 control treatments. In the following, a block for the remaining treatment allocations will be used.

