7.3 Assignment to Study Groups

A two-staged randomization scheme will be used. The first block will contain a total of 20 patients. The second block will contain a total of 36 patients. For each block, a container with sealed envelopes with paper cards for the group assignment (equally sized groups) will be prepared. At final inclusion of a patient, one sealed envelope will be drawn from the container and the patient will be assigned accordingly. After assignment, the paper cards are sealed again and stored in the patients case report file.

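### Allocation is balanced 1:1 within two successive blocks, but the primary test ignores the block; if the blocks differ by a shift common to both arms, the test is mildly conservative and loses a little power

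*Combined protocol and SAP*

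**What the plan says.** **Allocation.** Section 6.3.1 states that "the first block will contain 10 interventional and 10 control treatments", so that the arms are suitably distributed for the interim analysis. Section 7.3 gives the sizes: "The first block will contain a total of 20 patients. The second block will contain a total of 36 patients". Each container holds equal numbers of cards for the two arms, so the second block is 18:18. The containers are used one after the other.

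**Primary analysis.** Section 11.4.2 tests relative change in femoral tunnel volume from baseline to Visit 5. After a Kolmogorov-Smirnov check, "In case the assumption of normality holds, a Student's t-test is performed to test for a significant difference in means between the two groups"; otherwise a Mann-Whitney U test is used. Neither uses the block.

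**Secondary model.** The candidate covariates in 11.4.2.1 are sex, age, preinjury Tegner score and associated injury. The block is not among them. No section plans a stratified analysis or explains why the block is left out.

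**Sample size.** Section 11.2: "It is aimed to detect a 20% difference in relative change of bone tunnel volume between the two groups". The SD is 25.175%, alpha is 0.05 and target power is 0.8. This gives 25 per arm, and 56 in total after 10% drop-out.

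**The concern.** The design builds a stratum into the allocation and the analysis then drops it. Because the arms are equal within each block, a level difference between blocks that affects both arms alike cannot move the arm difference. It does add to the spread within each arm, and the two-sample t-test takes its standard error from that spread. The nominal standard error is then larger than the true sampling error of the arm difference. The confidence interval is wider than it need be, the real type I error is below 5%, and some power is given away. The Mann-Whitney branch has the same weakness, because block differences remain in the ranks.

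All of this depends on the blocks actually differing. At stake is a small amount of efficiency in a trial with little to spare: drop-outs are not replaced (11.6), and recruitment is planned over 22 months (6.2).

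**Working it through.** **Inputs from the documents.** Difference 20 points, SD σ = 25.175, two-sided alpha 0.05, 25 evaluable per arm (11.2, 11.4); blocks of 10+10 and 18+18 (6.3.1, 7.3).

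**Assumptions.** The shift δ between blocks is not in the documents, so a range is used. The 25 completers per arm are taken as 9 from block 1 and 16 from block 2, that is, 10% loss spread evenly.

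**Step 1: the plan's own figure.** n = 2(1.960 + 0.842)² × (25.175/20)² = 15.70 × 1.584 = 24.9, so 25 per arm. Then 50/0.9 = 55.6, so 56. Both reproduce. This is the normal approximation; the exact noncentral t gives 78.6% power at 25 per arm, which is the baseline below.

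**Step 2: error term.** With a share p of each arm in block 1, the within-arm variance becomes about σ²[1 + p(1−p)(δ/σ)²]. With p = 9/25, p(1−p) = 0.2304.
- δ = 10: (10/25.175)² = 0.158; variance factor 1.036; SD up 1.8%.
- δ = 20: (20/25.175)² = 0.631; variance factor 1.145; SD up 7.0%.

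**Step 3: power and type I error, shift added to σ.** Under a common shift the arm difference keeps mean 20 and standard error 25.175 × √(2/25) = 7.12. The pooled sum of squares divided by σ² follows a noncentral chi-square with 48 df and noncentrality 2 × (9×16/25) × (δ/σ)², which is 1.8 at δ = 10 and 7.3 at δ = 20. Integrating the rejection probability over that distribution gives the plain test. The model with a block term has 47 df and does not depend on δ.

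| Assumed common shift (points) | Plain t-test power | Power with block term | Plain t-test type I error |
|---|---|---|---|
| 0 | 78.6% | 78.6% | 5.0% |
| 10 | 77.5% | 78.6% | 4.6% |
| 20 | 74.1% | 78.6% | 3.6% |

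Type I error with the block term is 5% throughout. Simulation with the same inputs agrees to about half a point (plain power 78.5 / 77.6 / 74.6%; type I error 5.0 / 4.5 / 3.7%). With no shift, the block term costs less than 0.1 point of power.

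**Step 4: the other reading of the SD.** If 25.175 is the total SD with the shift already inside it, the within-block SD is √(25.175² − 0.2304δ²), which is 24.71 at δ = 10 and 23.27 at δ = 20.

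| Shift (points) | Plain t-test power | Power with block term |
|---|---|---|
| 10 | 79.0% | 80.0% |
| 20 | 80.2% | 84.5% |

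Planned power is kept, and the gain of about 1 and 4 points is only relative.

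**Step 5: a shift in the intervention arm only.** If block 1 intervention patients do worse by 10 or 20 points, the arm difference falls to 20 − 10 × 9/25 = 16.4 or 20 − 20 × 9/25 = 12.8. Simulated power is about 61.0% (plain) against 61.2% (block term), and 39.2% against 40.5%. The block term recovers little here.

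**The case against.** The strongest reply is that nothing in the documents shows a drift common to both arms. This is one centre, and the blocks exist to serve the interim analysis, not because enrolment order is thought prognostic. Every non-zero loss above comes from an assumed shift, and a 20-point shift is as large as the target effect. At 10 points the loss is about one power point. Section 11.2 also calls 25.175% an overall SD, so the plan may already allow for such variation. All of this stands, and it limits the point to a small one.

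Three stronger readings are tempting, and the documents support none of them.

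- **A reader might infer that the primary test is invalid or yields too many false positives.** The error runs the other way: the real type I error is at or below 5%.
- **A reader might infer that a learning curve with the new technique is the drift in question.** Controls receive the in-house standard technique (3.5, 6.1), so such an effect would fall mainly on the intervention arm. Step 5 shows that it would then move the arm difference, and that a block term would not correct it. Section 3.6 also reports full cadaver runs with the team beforehand.
- **A reader might infer that the interim look separates the blocks.** At 2.52 patients a month (6.2), block 1 fills at 20/2.52 = 7.9 months and its last patient reaches Visit 4 at about 12.4 months. By then about 12.4 × 2.52 = 31 patients are enrolled, so some 11 block 2 patients precede that look.

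One point favours the block term beyond efficiency. The cancellation is exact only while both arms keep the same share of each block. Sections 7.4 and 8.8 remove patients with re-rupture or with complications during surgery using the product. As an illustration, suppose block 1 keeps 7 intervention and 10 control patients, block 2 keeps 18:18, and the shift is 20 points. The plain estimate then moves by 20 × (10/28 − 7/25) = 1.5 points. A block term removes this if the shift is common to both arms.

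**Conclusion.** The point holds as a minor, conditional one. The analysis does not follow the restricted randomisation. If the blocks differ by a shift common to both arms, the plain test is mildly conservative: about 1 power point is lost at a 10-point shift and about 4 at 20 points, with 25 per arm and the shift added to the planned SD. If the planned SD is the total SD, nothing is lost against plan and the same amounts are only forgone gains. With no shift there is no defect. The size rests on an assumed drift, on equal retention by block in both arms, and on normal data with equal variances. A block term would not remove drift inside the 36-patient block. The case for changing the plan is that the change is almost free, not that the trial's conclusion is at risk.

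**What to change.** In 11.4.2, make the primary comparison a linear model of relative volume change on arm plus allocation block (1 or 2), and report the adjusted mean difference with its 95% CI. If the rank branch is kept, replace the Mann-Whitney U test with a van Elteren test stratified by block. Add a descriptive table of the arm difference by block, since an effect of early experience confined to the intervention arm would show there and is not corrected by the block term. Using the same term for the Visit 4 supportive analysis and the secondary outcomes is optional.

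The cost is a wording change in the statistical section and one degree of freedom, under 0.1 point of power if the blocks do not differ. The block is known from the allocation record, so no new data are needed.
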